To facilitate a systematic and patient-centered approach to delivering services and resources to address the unmet needs of adolescents and young adults (AYAs) with cancer, we developed in preliminary studies the AYA Needs Assessment & Service Bridge (AYA NA-SB). AYA NA-SB includes (1) a holistic PROM assessing AYAs' physical, psychosocial and practical needs and (2) a collection of referral pathways for connecting AYAs to services and resources based on the needs they report (see **Appendix A**). To optimize AYA NA-SB's usability (i.e., ease of use) and usefulness (i.e., link to services), promote cancer programs' receptivity to AYA NA-SB implementation, and anticipate implementation strategies needed to facilitate AYA NA-SB's successful implementation and sustainment, we conducted usability testing, an ethnographic user and contextual analysis, and iterative prototyping workshops with a multidisciplinary design team.

Our development process culminated in an intervention with high usability and usefulness, characteristics we expect to promote AYA NA-SB's successful implementation and achievement of desired outcomes; however, AYA NA-SB's implementation and efficacy remain untested. Thus, through this study, we will evaluate AYA NA-SB's implementation and establish proof-of-concept. To avoid creating a tool that is only applicable to its high-resource testing environment, I will also plan for AYA NA-SB's potential scale-up across diverse health systems serving AYAs with cancer.

Objectives

Aim 1. Assess the implementation of AYA NA-SB. I will pilot AYA NA-SB in the North Carolina Cancer Hospital (NCCH), with a primary focus on implementation outcomes.

Aim 2. Establish proof-of-concept for AYA NA-SB. I will use pilot data to generate preliminary evidence on the extent to which AYA NA-SB addresses AYAs' reported needs.

Aim 3. Plan for AYA NA-SB's scalability and sustainability in diverse health systems. I will conduct annual 60-minute semi-structured qualitative interviews with AYA providers and program leaders from approximately 8 health systems to proactively address challenges and prepare for future AYA NA-SB scale-up and sustainability.

Methods and Measures

Design

- Aim 1/2: Single-arm feasibility pilot
- Aim 3: qualitative interviews

Setting

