Aim 1/2: I will pilot AYA NA-SB in the North Carolina Cancer Hospital (NCCH). NCCH is a public, National Cancer Institute-designated Comprehensive Cancer Center located in central North Carolina, in a relatively metropolitan area. At NCCH, around 450 individuals ages 15-30 are diagnosed each year. About one third of these patients are treated in pediatric oncology and the remainder in adult oncology. NCCH's AYA program was established in 2015 with funding from a local nonprofit organization, the BeLoud Sophie Foundation. This funding was initially allocated towards hiring one fulltime employee (a social worker/program director) to provide AYA-specific care at NCCH. Since 2015, the program has evolved, hiring new AYA-specific staff members (e.g., nurse practitioner, fertility counselor) and expanding program activities and reach.

Aim 3: I will conduct interviews with providers and program leaders from AYA programs around the country.

Subjects selection criteria

• Inclusion Criteria

Aim 1/2: AYAs with cancer ages 18 through 39 currently in treatment at NCCH Aim 3: AYA providers and program leaders from around the country

• Exclusion Criteria

No exclusion criteria

• Sample Size

- Aim 1/2
 - \circ N=25-50 AYAs
 - o N=25/arm has been proposed as the minimum threshold of sample size for aims related to instrumentation. ¹⁸ Given that this is a single-arm pilot study, we have determined that a sample size between 25 and 50 is appropriate.
- Aim 3
 - N=8 AYA providers/ program leaders. Interviewees will be purposefully sampled such that
 they represent a range of health systems. As such, a sample size of 8 is expected to yield
 adequate data to meet the objectives of Aim 3.

Interventions and Interactions

Intervention (Aims 1, 2)

The intervention, AYA NA-SB, includes three components: (1) a needs assessment, (2) a map of referral pathways, and (3) implementation guidance (**Appendix A**).

Needs assessment. The needs assessment portion of AYA NA-SB is a 57-item PROM which includes nine domains: (1) information, (2) cancer care team, (3) physical health, (4) emotional health, (5) sexual and reproductive health, (6) health behaviors and wellness, (7) work and education, (8) peer support and programming, and (9) finances and everyday needs.

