	Prevalence of needs by follow demographic/clinical variable	$\operatorname{ss}(?)$		
Services rendered	reported needs	ays initiated in response to AYAs'	Providers	Fidelity Checklist
	needs reported by AYAs	esources rendered in response to	AYAs	Postintervention AYA survey
Care coordination	The delivery of multidisciplinary services to address needs reported by AYAs	AYA's receipt of services/ resources from across disciplines to address reported needs within one month of needs assessment completion	AYAs	Postintervention AYA survey
Needs met	Extent to which services and resources received met reported needs	AYAs' perception of the degree to which their needs were adequately addressed during the study period	AYAs	Postintervention AYA survey

Analytical Plan

Aim1. I will report descriptive

statistics on demographic and clinical variables. I will also calculate descriptive statistics on all quantitative implementation outcomes. Index scores will be generated for each measure by calculating an unweighted average of items within each construct. Further, I will conduct bivariate analyses to assess whether implementation outcomes vary by demographic and clinical variables to ensure that AYA NA-SB is feasible, acceptable, and appropriate across patient characteristics.

Qualitative interview data will be analyzed using template analysis²¹ based on a priori themes (i.e., Proctor's model and CFIR constructs) but allowing for additional emergent themes. A peer and I will independently abstract data from interview transcriptions per Proctor outcomes and CFIR constructs and discuss discrepancies until consensus is reached. When necessary, a third party will be pulled in to resolve discrepant coding.

Aim 2. I will calculate descriptive statistics on AYAs' identified needs, reporting the prevalence of specific needs and needs within specific domains, as well as on services received. I will also calculate descriptive statistics on quantitative service and patient outcomes. I will conduct bivariate analyses to assess whether service and patient outcomes vary by demographic and clinical variables.

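### Aim 1 uses subgroup comparisons in 25-50 AYAs to ensure the tool works across patient characteristics, but finding no variation at that size cannot support this

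*Combined protocol and SAP*

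**What the plan says.** Under Objectives, Aim 1 is to pilot AYA NA-SB "with a primary focus on implementation outcomes". The Design section calls the study a "Single-arm feasibility pilot".

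The patient-rated outcomes are the acceptability, appropriateness and feasibility scales (AIM, IAM, FIM) in Appendix C. Each has four items scored 1 to 5. The Analytical Plan scores them simply: "Index scores will be generated for each measure by calculating an unweighted average of items within each construct". It then adds the comparison at issue: "I will conduct bivariate analyses to assess whether implementation outcomes vary by demographic and clinical variables", with the purpose "to ensure that AYA NA-SB is feasible, acceptable, and appropriate across patient characteristics".

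On size, the Sample Size section says that 25 per arm "has been proposed as the minimum threshold of sample size for aims related to instrumentation", and concludes that "we have determined that a sample size between 25 and 50 is appropriate".

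The plan names no test, significance level, confidence interval, equivalence margin, minimum group size, or scale score that would count as feasible or acceptable. Aim 2 plans the same kind of comparison for service and patient outcomes, but attaches no such purpose to it.

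**The concern.** The purpose clause asks the comparison to deliver an assurance, and there are two separate reasons why it cannot.

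1. **Logic.** Testing whether scores vary between groups says nothing about whether each group's score is good enough. Uniformly low scores would show no variation. This holds at any sample size.
2. **Size.** With 25 to 50 people, a real moderate gap will usually go undetected, so failing to see variation is weak evidence that there is none.

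The risk is that a table of non-significant comparisons is read as showing that the tool suits every patient group. These outcomes are the main focus of Aim 1. The Aim 3 procedure also has pilot data reviewed with providers from other health systems in preparation for scale-up, so an over-reading would have an audience.

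**Working it through.** **The plan's own figure.** N=25-50 cannot be re-derived. The Sample Size section gives a cited minimum and no power, precision, SD or effect size.

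**Inputs.**
- From the documents: total N of 25 and 50; outcomes that are averages of items scored 1 to 5.
- Assumed, because the plan is silent: two-sided 5% two-sample t-test, 80% power as the yardstick, every participant answering the one-month survey, benchmark gaps of 0.5 and 0.8 SD, and splits of 50/50 and 20/80.

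**Formulas**, in SD units, with df = n1+n2−2:
- Standard error of a difference: SE = √(1/n1 + 1/n2)
- 95% CI half-width for a difference: t(0.975, df) × SE
- Power for a gap d: noncentral t with noncentrality d/SE
- 95% CI half-width for one group mean: t(0.975, n−1)/√n

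Worked example, 12 v 13: SE = √(1/12 + 1/13) = 0.400; t(0.975, 23) = 2.069; half-width = 2.069 × 0.400 = 0.83 SD. For 25 v 25: SE = 0.283; t(0.975, 48) = 2.011; half-width = 0.57 SD.

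| Split | Detectable at 80% power | Power, 0.5 SD | Missed, 0.5 SD | Power, 0.8 SD | 95% CI half-width |
|---|---|---|---|---|---|
| 12 v 13 | 1.17 SD | 22% | 78% | 48% | 0.83 SD |
| 25 v 25 | 0.81 SD | 41% | 59% | 79% | 0.57 SD |
| 5 v 20 | 1.46 SD | 16% | 84% | 34% | 1.03 SD |
| 10 v 40 | 1.01 SD | 28% | 72% | 60% | 0.71 SD |

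**Could the data positively exclude a gap?** Suppose two groups are truly identical. By simulation (normal scores, SD estimated), the chance that the whole 95% CI for the difference lies inside the margin is:

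| Split | Inside ±0.5 SD | Inside ±0.8 SD |
|---|---|---|
| 12 v 13 | under 0.1% | 8% |
| 25 v 25 | 1% | 58% |
| 5 v 20 | under 0.1% | under 1% |
| 10 v 40 | under 0.1% | 21% |

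The first column is small because every half-width in the previous table exceeds 0.5 SD. The interval fits inside ±0.5 SD only when the sample SD happens to come out low.

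**Yardstick.** The smallest totals with 80% power for 0.5 SD are 128 (64 v 64) and 200 (40 v 160). They show scale only and are not a proposal to enlarge the pilot.

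**How well is each group's own mean known?** Half-widths are 0.41 SD with 25 respondents, 0.64 SD with 12, 0.72 SD with 10 and 1.24 SD with 5.

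**Direction of the assumptions.** Survey non-response would weaken all of this: at 10 v 10 respondents, power for 0.5 SD falls to 19%. Diagnosis and race/ethnicity have more than two categories. The recruitment section seeks variety in cancer type, sex and race/ethnicity but sets no minimum per group, so small groups are likely.

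**The case against.** **The clause states a motive, not a decision rule.** The operative verb is to assess whether outcomes vary, and no section says that a null result will be read as consistency. The design is openly a pilot, descriptive statistics come first, and provider interviews cover the same constructs. This is fair, and it is why the point is minor. But nothing qualifies the purpose, the interviews give no patient subgroup scores, and the plan offers no other quantitative basis for the assurance.

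**A 0.5 SD gap may not matter.** If the SD on the 1-5 scale were 0.5 points (an assumption), 0.5 SD is 0.25 points, for example 4.50 against 4.25, with both groups above Agree. Adequacy across groups is not equality of groups, so precision of each group's mean is the more relevant measure. With 25 in a group that precision may be usable: 0.41 SD is about 0.2 points at an SD of 0.5 and 0.4 points at an SD of 1.0. This stands for large groups. For a group of 5 the half-width is about 0.6 to 1.2 points on the same assumptions. The objection also confirms that the planned comparison is the wrong tool for the stated purpose.

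**The 95% interval is stricter than usual equivalence practice.** With the 90% interval used in two one-sided tests, the chance of excluding 0.5 SD is about 0.2% at 12 v 13 and 10% at 25 v 25, and 0.8 SD is excluded 75% of the time at 25 v 25. So exclusion of a moderate gap at N=50 is unlikely rather than near impossible. The conclusion does not change.

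**Some analyses would do better.** Age could be kept continuous: a correlation of 0.4 has about 83% power at N=50, though 51% at N=25. At 25 v 25, power is 79% for 0.8 SD and 93% for 1.0 SD. Very large differences in a balanced characteristic would usually be seen at the upper N.

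**Conclusion.** The concern holds, as a minor point. The logical part needs no assumptions: testing for variation cannot establish that each group finds the tool feasible, acceptable and appropriate. The size part rests on the assumed t-test, benchmarks and two-group splits. Under every split shown, a true 0.5 SD gap is missed more often than found (59% to 84%), and identical groups could rarely be shown to lie within 0.5 SD of each other. The pilot's size is reasonable for a pilot. What needs changing is the conclusion that the Aim 1 text invites from it.

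**What to change.** Replace the Aim 1 sentence on bivariate analyses with text such as:

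> Bivariate analyses of implementation outcomes by demographic and clinical variables will be exploratory and descriptive. For AIM, IAM and FIM, I will report the number of respondents, mean and 95% CI in each group, and differences between groups with 95% CIs. A lack of observed difference will not be read as showing that AYA NA-SB is equally feasible, acceptable or appropriate across groups.

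The cost is three sentences in the Analytical Plan and confidence intervals in the tables, with no new data or participants. The claim becomes more modest, and small groups will show wide intervals; a group of one has none. The change sets no score for adequacy. It lets readers judge each group's mean and its uncertainty, which the comparison alone does not.

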Appendix A: AYA NA-SB

AYA NA-SB

AYA NEEDS ASSESSMENT & SERVICE BRIDGE

Needs Assessment 1. INFORMATION

	I want more information about:	Agree	Somewhat agree	I have enough information about this concern	Not sure
1	My cancer diagnosis				
2	The short-term side effects of treatment				
3	The long-term side effects of treatment				
4	What will happen when treatment finishes				
5	My disease status				
6	My test results				
7	What to do if I have side effects from my treatment				
8	How my genetics may or may not have impacted my diagnosis and treatment				

2. CANCER CARE TEAM

	I want my cancer treatment team to do a better job of:	Agree	Somewhat agree	My cancer treatment team is doing this already	Not sure
9	Respecting me as an individual, not just a cancer patient				
10	Offering to talk to me in private, without my family or friends				
11	Explaining what they were doing in a way I can understand				
12	Encouraging me to ask questions				
13	Engaging me in decision-making about my treatment and respecting my				
	decisions				
14	Asking me about my treatment concerns				

3. PHYSICAL HEALTH

		Адмоо	Somewhat	I have	Not sure
		Agree	Somewhat		Not sure
	I want more help with:		agree	enough help	
				with this	
				concern	
15	Managing pain				
16	Managing my medications				
17	Managing physical side effects of treatment				
18	Managing feeling tired/ fatigued				

19	Managing loss of walking ability		

4. EMOTIONAL HEALTH

	I want more help with:	Agree	Somewhat agree	I have enough help with this concern	Not sure
20	Feeling anxious or scared				
21	Feeling depressed				
22	Having what I need to cope with my diagnosis				
23	Worrying about my cancer spreading				
24	Worrying about my cancer returning or getting another type of cancer				
25	Worrying about how my family is coping				
26	Coping with changes in my dating or romantic life				
27	Coping with changes in my relationships with my family members				
28	Coping with changes in my relationships with friends				
29	Feeling independent				
30	Coping with changes in my physical ability				
31	Coping with changes in my appearance				
32	Coping with not being able to do the same things as other people my age				
33	Managing the emotional side effects of treatment				
34	Being able to make plans or think about the future				

5. SEXUAL & REPRODUCTIVE HEALTH

	I want more information about:	Agree	Somewhat agree	I have enough information about this concern	Not sure
35	My risk of infertility and my fertility preservation options				
36	Treating infertility and other options for having children in the future (i.e., sperm/egg freezing, artificial insemination, in vitro fertilization, surrogacy, adoption, etc.)				
37	Sexuality and intimacy during cancer treatment				
38	Sexual side effects of my treatment (e.g., sexual dysfunction)				
39	The effects of treatment on long-term hormone changes				

6. HEALTH BEHAVIORS & WELLNESS

	Agree	Somewhat	I have	Not sure
I want more information about:		agree	enough	

			information about this concern	
40	Nutrition		concern	
41	Exercise or physical activity			
42	Getting enough or better-quality sleep			
43	Smoking or vaping during cancer treatment			
44	Drug or alcohol use during cancer treatment			
45	Spiritual support or resources			
46	Alternative therapies (herbal treatment, acupuncture, massage therapy, meditation, etc.)			

7. WORK & EDUCATION

	I want more help with:	Agree	Somewhat agree	I have enough help with this concern	Not sure
47	Managing my school life while going through cancer treatment				
48	Managing my work life while going through cancer treatment	_			

8. PEER SUPPORT & PROGRAMMING

[figure not shown]
		Agree	Somewhat	I have enough	Not sure
	I want more help with:		agree	help with this	
				concern	
49	Being able to spend time with people my own age				
50	Being able to talk to people my own age who have been through a similar				
	cancer treatment experience				
51	Participating in social activities				

9. FINANCES & EVERYDAY NEEDS

	I want more help with:	Agree	Somewhat agree	I have enough help with this concern	Not sure
52	Paying my bills				
53	Scholarship or loan repayment options				
54	My health insurance (e.g., access/eligibility, coverage, cost)				
55	Getting to and from my cancer care appointments				
56	Having childcare during my cancer care appointments	·			
57	Having stable housing	·	·		-

ase indicate anything else you want help with, below:	

Map of referral pathways

Implementation Guidance

1	Consider a phased-in approach to implementation, for example, by implementing within one disease group and
	expanding outwards
2	Build buy-in by engaging in implementation planning any provider groups who will interface with AYA NA-SB
	in practice
3	Build buy-in among leadership, emphasizing the potential benefits of AYA NA-SB for patient care, patient-
	provider communication, provider-provider communication, and program development
4	Provide education across disease groups and identify champions within each disease group to facilitate referrals of
	AYAs to AYA program
5	
3	Obtain a thorough understanding of services and resources available at your institution prior to implementation,
	identifying gaps that may hinder follow-up on needs reported by AYAs on the needs assessment. For identified
	gaps, bolster existing services or tailor the needs assessment to address the subset of needs that your institution has
	the capacity to address.
6	Explicitly outline referral pathways for each follow-up domain, identifying primary contacts, current workflow,
	and best method of communication for service/resource providers.
7	Where possible, leverage existing communication and documentation channels in AYA NA-SB delivery. Modify
	communication and documentation processes as needed to allow for, at a minimum, traceable documentation of
	follow-up on needs.
8	Leverage staff who are currently assessing and addressing the needs of AYA patients at your institution and thus,
	have the necessary expertise and time allocated towards these tasks.
9	Identify approach for ensuring that services and resources are provided in a timely manner once needs are
,	identified.
10	
10	Use pilot testing to tailor AYA NA-SB to your institution, for example, to:
	Make additional refinements to the needs assessment tool to tailor it to your institution
	• Determine frequency of needs assessment administration that makes sense in your institution (e.g., 1
	month versus 3 months)
	Map out changes needed to your institution's EHR to facilitate systematic documentation
	- Map out changes needed to your institution's Erric to identitude systematic documentation

Appendix B: Fidelity checklist

Assessment ID					
(see top of assessment)					
Assessment Date (see timestamp at top of			/ /		
assessment)				-	
Date I reviewed assessment			//	_	
Date in which I initiated referral pathways			//	_	
Referral pathways initiated	Need # Referral Pathway				
For needs indicated by this	Completely	Disagree	Neither agree	Agraa	Completely
AYA, I was confident about	disagree	Disagree	nor disagree	Agree	agree
which referral pathways to initiate	0	2	3	4	S

Appendix C: Postintervention AYA survey

Acceptability of Intervention Measure (AIM)

	Completely disagree	Disagree	Neither agree nor disagree	Agree	Completely agree
1. The needs assessment meets my approval.	①	2	3	4	(5)
2. The needs assessment is appealing to me.	①	2	3	4	(5)
3. I like the needs assessment.	①	2	3	4	(5)
4. I welcome the needs assessment.	①	2	3	4	(5)

Intervention Appropriateness Measure (IAM)

	Completely disagree	Disagree	Neither agree nor disagree	Agree	Completely agree
1. The needs assessment seems fitting.	①	2	3	4	(5)
2. The needs assessment seems suitable.	①	2	3	4	(5)
3. The needs assessment seems applicable.	①	2	3	4	(5)
4. The needs assessment seems like a good match.	①	2	3	4	(5)

Feasibility of Intervention Measure (FIM)

	Completely disagree	Disagree	Neither agree nor disagree	Agree	Completely agree
1. The needs assessment seems implementable.	①	2	3	4	(5)
2. The needs assessment seems possible.	①	2	3	4	(5)
3. The needs assessment seems doable.	①	2	3	4	(5)
4. The needs assessment seems easy to use.	①	2	3	4	(5)

Face validity/ content validity

	Completely disagree	Disagree	Neither agree nor disagree	Agree	Completely agree
1. The needs assessment helped me to communicate my needs.	1	2	3	4	(5)
2. The needs assessment was relevant to me.	①	2	3	4	(5)
3. The needs assessment included all needs that I was concerned about.	•	2	3	4	\$

Usability

e successive y					
	Completely disagree	Disagree	Neither agree nor disagree	Agree	Completely agree

1. I think that I would like to complete the needs assessment again.	①	2	3	(4)	(5)
2. I found the needs assessment too complicated.	①	2	3	4	(5)
3. I think the needs assessment was easy to complete.	①	2	3	4	(5)
4. I think I would need help to complete the needs assessment.	①	2	3	4	(5)
5. I felt very confident completing the needs assessment.	1	2	3	4	(5)

Usefulness

	Completely disagree	Disagree	Neither agree nor disagree	Agree	Completely agree
1. The needs assessment provided a helpful way for me to tell my doctors what I need.	①	2	3	4	(5)
2. I did use or would use services and resources offered to me by my doctors based on the needs I checked in the needs assessment.	•	2	3	4	⑤

Care coordination/Needs met

	Yes	No
1. I reported no needs on the needs assessment	① (skip to end)	©
2. I received follow-up care for the needs I reported (e.g., referrals, counseling, other services or resources)	0	② (skip to end)

3. Please indicate the type of follow-up care that you received. (check all that apply)

(1) communication from my primary oncology team
(2) a phone call or visit from a social worker
(3) a phone call or visit from a nurse navigator
(4) A referral to a specialist (e.g., fertility counselor, nutritionist, physical therapist, etc.)
(5) educational materials
(6) other

	Completely disagree	Disagree	Neither agree nor disagree	Agree	Completely agree
4. The follow-up care I received addressed my needs.	①	2	3	4	(5)

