Referral pathway initiation. Within seven calendar days of AYA NA-SB completion, the implementation leader will review completed needs assessments and, depending on AYAs' preferences indicated at the end of the needs assessment, will either (a) initiate appropriate referral pathways, or (b) provide a list of recommended referrals to AYAs. For each needs assessment reviewed, they will document these actions on a brief fidelity checklist which timestamps their completion of these tasks, documents the referral pathways selected, and gauges their confidence in selecting appropriate referral pathways (**Appendix B**). This process is expected to take less than 10 minutes/ needs assessment.

Postintervention AYA survey. One month following their completion of the needs assessment, I will engage AYA pilot participants in an online postintervention survey (**Appendix C**) assessing their perceptions of AYA NA-SB's feasibility, acceptability, and appropriateness. In addition to items assessing AYAs' perspectives of the needs assessment itself, this survey will solicit information about the follow-up care AYAs received in response to needs they reported in the needs assessment and whether they felt their needs were met (Aim 2). This survey will administered through RedCAP and will take approximately 15 minutes to complete. AYAs will receive a second \$15 incentive for completing the postintervention survey.

Postintervention provider interview. I will conduct a semi-structured interview with the implementation leader and other participating providers from NCCH after AYA NA-SB has been administered to a minimum of n=15 AYAs. The purpose of this 1-hour interview is to assess provider perceptions of the feasibility, acceptability, and appropriateness of AYA NA-SB and to elicit information about perceived implementation determinants and strategies deployed. Interviews will be recorded and transcribed for analysis. **Appendix D** contains the interview guide.

Activity	Provider Training	Needs assessment administration	Referral pathway initiation	Postintervention AYA survey	Postintervention provider interview
Time	0	+6 weeks	+7 weeks	+10 weeks	+10-15 weeks

Instruments & procedure (Aims 3)

I will conduct annual semi-structured qualitative interviews with AYA providers and program leaders from diverse health systems to proactively address challenges and prepare for future AYA NA-SB scale-up and sustainability.

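### Young adults who report needs but get no follow-up care are never asked whether their needs were met, so the needs-met result covers recipients only

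*Combined protocol and SAP*

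**What the plan says.** The Needs met row of the Outcome Measure(s) table describes the outcome in two ways. The Definition column gives "Extent to which services and resources received met reported needs", which presupposes that something was received. The Measure column gives the AYA's "perception of the degree to which their needs were adequately addressed during the study period", with no such condition. The Postintervention AYA survey section says the survey will ask about follow-up care received and also "whether they felt their needs were met (Aim 2"). Aim 2 under Objectives reads "I will use pilot data to generate preliminary evidence on the extent to which AYA NA-SB addresses" AYAs' reported needs.

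Appendix C turns this into four items:

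- **Item 1:** AYAs who say they reported no needs leave the block.
- **Item 2:** "I received follow-up care for the needs I reported (e.g., referrals, counseling, other services or resources"). The No response carries an instruction to skip to the end.
- **Item 3:** type of follow-up care received.
- **Item 4:** "The follow-up care I received addressed my needs", on a 5-point agreement scale. No other item in the block asks whether needs were met.

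For analysis, the Aim 2 paragraph of the Analytical Plan promises descriptive statistics on service and patient outcomes and adds: "I will conduct bivariate analyses to assess whether service and patient outcomes vary by demographic and clinical variables". It gives no denominator for needs met and no rule for AYAs who were skipped past item 4.

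**The concern.** AYAs who report needs and receive nothing are the group in whom the intervention has most plainly not delivered, and they are the group removed from the needs-met outcome. A result confined to recipients says how well follow-up worked for those who got it. Aim 2 asks how far reported needs were addressed.

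Two consequences follow. First, the item 4 result is insensitive to reach: it can look equally good whether most or few AYAs receive follow-up. Second, the planned comparisons of needs met across demographic and clinical groups can show no difference between groups that differ in follow-up.

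The answers not collected at one month cannot be reconstructed. A No on item 2 also need not mean an unmet need. Under Referral pathway initiation, an AYA may prefer that the implementation leader "provide a list of recommended referrals to AYAs" instead of starting the referrals. Such an AYA might answer No and still have resolved the need unaided. The survey cannot separate these AYAs from those whose needs stayed unmet.

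**Working it through.** The plan states no needs-met figure to reproduce. The sample size of 25 to 50 comes from a cited minimum for instrumentation aims and has no rate or power behind it. The skip pattern itself is established by the text. What follows shows what it could do to the result, using assumed rates.

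**Notation (all three rates assumed; none is in the documents)**

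- f = share of AYAs with needs who receive no follow-up
- p = share of recipients who agree with item 4
- q = share of non-recipients whose needs were met anyway

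The item 4 summary is p. The proportion among all with needs is (1 − f)p + fq. The difference is p − [(1 − f)p + fq] = f(p − q).

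**Range with p = 80%**

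| f | All with needs, q = 0 | All with needs, q = 25% | Item 4 minus all with needs |
|---|---|---|---|
| 10% | 72.0% | 74.5% | 8.0 to 5.5 points |
| 25% | 60.0% | 66.25% | 20.0 to 13.75 points |
| 40% | 48.0% | 58.0% | 32.0 to 22.0 points |

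**Insensitivity to reach, at N = 25.** Assume all 25 report a need and complete the survey, and 80% of recipients agree. The lower limit counts every non-recipient as not met, and the upper limit counts every one as met.

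| Receiving follow-up | Item 4 | Lower limit, all 25 | Upper limit, all 25 |
|---|---|---|---|
| 20 (80%) | 16/20 = 80% | 16/25 = 64% | 21/25 = 84% |
| 15 (60%) | 12/15 = 80% | 12/25 = 48% | 22/25 = 88% |
| 10 (40%) | 8/10 = 80% | 8/25 = 32% | 23/25 = 92% |

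The item 4 column does not move. With everyone receiving follow-up, the two summaries agree at 80%.

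**Worked example.** 40 AYAs with needs, 30 with follow-up, 24 agreeing:

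- recipients only: 24/30 = 80% (Wilson 95% CI 63% to 91%)
- all 40, no non-recipient's needs met: 24/40 = 60% (45% to 74%)
- all 40, every non-recipient's needs met: (24 + 10)/40 = 34/40 = 85% (71% to 93%)

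The collected data leave a 25-point range (85 − 60), quite apart from sampling error.

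**Group comparison.** Take two groups with p = 80% in each and follow-up of 90% and 60%. Item 4 shows 80% against 80%. Among all with needs:

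- q = 0: 0.9 × 80% = 72% against 0.6 × 80% = 48%, a gap of 24 points
- q = 25%: 72% + 0.1 × 25% = 74.5% against 48% + 0.4 × 25% = 58%, a gap of 16.5 points

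**The case against.** The strongest reply is that item 4 closely follows the protocol's own definition of needs met, which concerns services received. On that reading the firm defects are a disagreement between two cells of one row and an unstated denominator. The point about the Definition column is correct. But the Measure column, the survey purpose and Aim 2 carry no such limit, so a recipients-only reading leaves them without a measure.

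A second reply is that Aim 2 concerns what the intervention addressed, so anyone without follow-up can simply be counted as not addressed; items 1, 2 and 4 already give 24/40 in the example. That is a workable fallback, but the plan does not state it. It also replaces the AYA's own perception with an assumption, and it may misclassify those who chose only a list. Some of these may answer Yes to item 2, since it mentions other resources. Their stated preference should make them identifiable, but not whether their needs were met.

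Third, non-receipt is not concealed: item 2 records it, and it appears under services rendered and care coordination, including their group comparisons. This stands, and it confines the defect to needs met and its own comparisons.

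Fourth, the sizes are assumed, and the choice of q below p fixes the direction. This also stands. If q exceeded p, item 4 would understate: in the example with q = 100%, 0.25 × (80% − 100%) = −5 points. The calculation also reduces a 5-point scale to agreement, which the plan does not do. At this sample size a real gap would be hard to establish: for 72% against 48% with 20 per group, 1.96 × √(0.72 × 0.28/20 + 0.48 × 0.52/20) gives about ±29 points. Imprecision does not excuse leaving the question unasked.

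Finally, this is a single-arm pilot focused mainly on implementation outcomes, with no threshold attached to needs met. That limits the seriousness of the point without removing it.

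**Conclusion.** The concern holds. The skip on item 2 and the wording of item 4 restrict needs met to recipients of follow-up care, while Aim 2, the survey purpose and the Measure column are not so restricted. This follows from the text alone. That the result would be reported among those who answered item 4 is an inference from the absence of any stated denominator.

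The size depends entirely on assumed rates. With 80% agreement among recipients, 10% to 40% of AYAs with needs lacking follow-up, and 0% to 25% of those having needs met anyway, item 4 overstates the figure for all with needs by 5.5 to 32 points. The direction reverses if non-recipients fare better than recipients, and the difference vanishes if everyone receives follow-up. It should be fixed because it affects the only patient-reported measure of whether needs were met, and the missing answers cannot be obtained afterwards.

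**What to change.** 1. Remove the skip on item 2 as it applies to needs met. Show everyone who answers No to item 1 a question that does not presuppose follow-up, for example: My reported needs were addressed. Items 3 and 4 can stay limited to recipients.
2. State the denominator as all postintervention survey respondents who reported at least one need, and say how the 5-point response will be summarised.
3. Report item 4 among recipients as a secondary result, beside the proportion receiving follow-up. It keeps the link to the care received, which the new item does not, because the new item credits needs met by any route.
4. Add a sensitivity analysis counting No on item 2 as not addressed. Make this the main rule only if the survey can no longer be changed, and then label it a lower bound.
5. Reconcile the Definition and Measure columns of the Needs met row.

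Optionally, identify AYAs with needs from the needs assessment data instead of item 1. The plan would then have to say whether the Somewhat agree and Not sure responses count as a need.

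The cost is one added or reworded item, one REDCap branching edit, and one or two sentences in the outcome table and Analytical Plan. The needs-met figure may turn out less favourable.
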